3.1. Study strengths and limitations

When taken as prescribed, ET is successful in reducing the risk of BC recurrence (EBCTCG, 2011). However, suboptimal adherence and persistence are an issue with this medication. To date, efforts to improve ET adherence have had little success, mostly focusing on patient education or reminders to reduce the risk of forgetting medication (Heiney, Ekinci). Side effects have been identified as a consistent predictor of ET nonadherence (Moon et al., 2019; Cahir et al., 2015; Pan et al., 2018), and are more amenable to change than demographic or clinical predictors. However, a recent systematic review (Fleming et al., 2022) reported a lack of consensus on the influence of specific side effects on ET nonadherence, which inhibits the identification of appropriate, targeted intervention strategies. This pilot study will explore the influence of a targeted intervention for sleep problems (CBT-I) on self-reported ET adherence in a sample of BC survivors.

Previous efforts to improve ET adherence have focused mostly on reminders or patient education, with little success (Ekinci et al., 2018; Heiney et al., 2019). However, recent studies report that participants express a desire for support with self-management of side effects (Arch et al., 2022; Hall et al., 2022; Jacobs et al., 2022). Jacobs et al. (2021) reported that participants found sessions focused on self-management of ET side effects such as sleep difficulties, hot flashes, and pain most useful. However, to the best of our knowledge, no studies have attempted to enhance adherence by targeting specific side effects. The current study will therefore directly address a perceived lack of support with side effects expressed by BC survivors (Peddie et al., 2021), and address a gap in the literature by investigating a specific, targeted intervention which may improve ET adherence.

Sleep problems are one of the most common ET side effects (Colleoni et al., 2018; Boldyrev et al., 2021), and have been associated with fatigue, musculoskeletal pain, and vasomotor symptoms (Desai et al., 2017; Leysen et al., 2019). Therefore, insomnia is a prevalent,

transdiagnostic side effect which may present an appropriate target for intervention to relieve overall side effect burden and improve ET adherence. CBT-I is considered the gold standard gold-standard treatment for insomnia (Ma et al., 2021), and has been effective in this population before in reducing not only sleep, but also depression, anxiety, and fatigue (D'arico et al., 2016).

The current study will administer CBT-I in groups of approximately 5 participants, through videoconferencing. A recent meta-analysis found no significant difference between remotelydelivered and conventional face-to-face CBT-I and reported that remotely-delivered CBT-I may be slightly more efficacious in comparison to in-person treatment (Ma et al., 2021). This format also has the advantage of widening accessibility, removing the financial and practical burden of travelling to in-person sessions. Delivering the intervention using a group (rather than individual) format presents a time-efficient and cost-effective intervention (Garland et al., 2022), and also addresses preferences expressed by BC patients to receive support with side effects in a group setting, so that they can learn from their peers' experiences (Jacobs et al., 2020). Despite being the gold-standard treatment for insomnia, clinician and patient-level barriers have limited access to this intervention (Koffel et al., 2018; Savard et al., 2021). The mode of delivery utilised in the current study therefore widens accessibility of the intervention. Furthermore, A recent systematic review by Peddie et al. (2021) reported that BC survivors showed high motivation to continue treatment, and willingness to make lifestyle changes to reduce the burden of side effects and persevere with ET. This willingness to try different strategies to reduce side effect burden indicates that they may be receptive to behavioural intervention such as CBT-I.

In addition to the mode of delivery of intervention, the design of the current study presents another strength. This study uses a repeated measures waitlist control, which is ethical as we will not be denying treatment to any participants. However, this could also be representative of real-world health services where patients frequently face extended waiting times (Garland et al., 2021; Koffel et al., 2018). A waitlist control design has been questioned due to the possibility of 'waiting effect' where participants may wait to change their behaviours until they receive an intervention, therefore delaying improvements, which is a potential ethical concern (Garland et al., 2021). However, insomnia tends to exist as a chronic, persistent issue in cancer patients, meaning participants are unlikely to improve without appropriate treatment (Savard et al., 2011).

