2.2.1. Recruitment

We will aim to recruit a sample of 40 participants. A-priori power analysis was conducted using G*Power version 3.1.9.7 (Faul et al., 2007) to determine the minimum sample size required to test the study hypothesis using a repeated measures ANOVA (within-between interaction). Results indicated the required sample size to achieve 80% power for detecting a medium effect (significance criterion α =.05) was *N*=18. Therefore, the target sample size of *N*=40 is adequate to test the study hypothesis.

Recruitment will involve emailing participants of a previous study (UEC21/29) who indicated that they would be interested in participation in future research studies. We will contact individuals from this sample whose responses indicated they are nonadherent to their ET medication and experience significant sleep problems, informing them of the opportunity to take part in this study.

The initial email will briefly outline the nature of the study and include an information sheet with full study details. Those who are interested will be asked to respond to this initial email so that a screening interview can be scheduled.

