2.7 Analytic approach

Participants demographics and clinical characteristics will first be presented. Descriptive data will be presented for each outcome measure (MARS-5, SCI, GAD-7, PHQ-9, FFS and BESS subscales) and sleep diary variables at each of the 3 timepoints (baseline, post-intervention, and 12-week follow-up).

Hypotheses will be tested using a 2x3 mixed factorial ANOVA. Between-subjects factor will be group (intervention or control), and within-subjects factor will be timepoint (baseline, post-intervention, and 12-week follow-up). We will examine the main effect of group, timepoint and interaction of group and timepoint. If a significant main effect is found, subsequent comparisons will be made applying Bonferroni correction.

3. Discussion

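### CBT-I is delivered in groups of about 5 in one arm only, but the ANOVA treats all women as independent; if outcomes correlate within a therapy group, the nominal 5% test rejects too often

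*Combined protocol and SAP*

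**What the plan says.** On delivery, section 3.1 states: "The current study will administer CBT-I in groups of approximately 5 participants". It presents this format as a strength, partly because patients have expressed a preference "to receive support with side effects in a group setting, so that they can learn from their" peers. Section 2.5 has one PhD student deliver the intervention, and gives it to the waitlist arm only after the 12-week assessment.

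On analysis, section 2.7 states: "Hypotheses will be tested using a 2x3 mixed factorial ANOVA". It adds: "Between-subjects factor will be group (intervention or control", with timepoint as the within-subjects factor. Section 2.2.1 bases the sample size on the same model, "using a repeated measures ANOVA (within-between interaction", and sets the target: "We will aim to recruit a sample of 40 participants". Section 2.4 allocates 2:1, waitlist to intervention as worded.

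No therapy-group term, ICC, design effect or cluster-robust method appears anywhere. The strengths and limitations in section 3.1 do not mention dependence between women treated together.

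**The concern.** Women in one therapy group share the same sessions, the same discussion and the same peers. If that makes their outcomes more alike, the mean of the intervention arm varies more from trial to trial than the ANOVA error term allows. Up to week 12 the waitlist arm has no such groups, so the extra variation falls on one side of the comparison. Under the 2:1 allocation that is the smaller arm, which makes the effect larger than it would be with equal arms.

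What is at stake is how the p-values are read. The study is called a pilot, but it tests hypotheses at the 5% level. Section 3.2 says that a successful result would support remote CBT-I as a way to improve adherence. There is also a practical point. Therapy-group membership is easily captured during delivery, but if it is not recorded, no later analysis can allow for it.

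**Working it through.** **1. The plan's own figure.** Section 2.2.1 gives N = 18 for "80% power for detecting a medium effect (significance criterion α =.05"). For 2 arms and 3 visits the noncentral F calculation uses λ = f² × N × 3 / (1 − ρ) on 2 and 2(N − 2) degrees of freedom. Neither f nor the within-person correlation ρ is stated; I take medium as f = 0.25.
- ρ = 0.5: λ = 0.0625 × 18 × 3 / 0.5 = 6.75 on 2 and 32 df, power 59%; 80% power needs N = 28.
- ρ = 0.7: λ = 0.0625 × 18 × 3 / 0.3 = 11.25; N = 18 is obtained.

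So 18 can be neither confirmed nor called wrong. The calculation has no input for clustering. I carry ρ = 0.5 and 0.7 forward as the assumed range.

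**2. Layout.** 40 / 3 = 13.3, so about 13 treated and 27 waitlist. 13 / 5 = 2.6, so about 3 therapy groups, taken as 5, 4 and 4. The size-weighted mean group size is m = (25 + 16 + 16) / 13 = 57 / 13 = 4.385.

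**3. Standard error at a single visit.** Design effect in the treated arm: D = 1 + (m − 1) × ICC. Ratio of the true SE to the SE assuming independence: √[(D/13 + 1/27) / (1/13 + 1/27)].

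| Assumed ICC | D | SE ratio |
|---|---|---|
| 0.02 | 1.068 | 1.023 |
| 0.05 | 1.169 | 1.056 |
| 0.10 | 1.338 | 1.108 |

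**4. The planned test.** The 2x3 mixed ANOVA was simulated with no mean effect and normal data. A shared therapy-group effect was added at the two post-baseline visits in the treated arm only. With 40,000 to 100,000 runs per scenario, the Monte Carlo standard error is at most √(0.05 × 0.95 / 40,000) = 0.0011 near 5%, or about 0.1 percentage point. Type I error at nominal 5%, over ρ = 0.5 to 0.7:

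| Assumed ICC | Interaction, 13 v 27 | Arm main effect, 13 v 27 |
|---|---|---|
| 0 | about 5% | – |
| 0.02 | 5.5–6% | – |
| 0.05 | 6.5–7.5% | about 6% |
| 0.10 | 8–10.5% | about 7% |

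At ICC 0.05 the interaction figure is about 6–7% with 20 v 20, and about 5–6% if 27 were treated and 13 waitlisted.

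**5. The scale of the ICC matters.** The ICC in step 4 refers to a post-baseline score. With individual variance 1, the therapy-group variance is ICC / (1 − ICC), and the individual variance of a change score is 2(1 − ρ). At ICC 0.10 the group variance is 0.1111. The ICC on the change score is then 0.1111 / 1.1111 = 0.10 at ρ = 0.5, but 0.1111 / 0.7111 = 0.156 at ρ = 0.7. This is why the inflation rises with ρ, and why any sensitivity analysis must name its scale.

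**6. Can it be repaired with about 3 groups?** Multiplying the treated-arm variance by D at a fixed ICC estimates no cluster variance. For a two-arm comparison at one visit it brought the error to 5.0% when true and assumed ICC were both 0.05, and to 5.2% when both were 0.10. A check on the change score left slightly more excess, still under 1 percentage point. Estimating from the groups themselves does less well: a test on therapy-group means with Satterthwaite degrees of freedom ran at 6.4–7.6%. For a 1 SD shift at ICC 0.05 and ρ = 0.5, its power was 63%, against 84% for the unadjusted ANOVA.

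**The case against.** The strongest reply is that nothing in the documents shows that adherence clusters by therapy group. One student delivers every session, so differences between therapists do not arise. The listed session content is about sleep, whereas the primary outcome is self-reported tablet-taking. The sentence on learning from peers reports what patients prefer; it does not say that their MARS-5 scores will move together. A small ICC fits the text at least as well as 0.10, and at 0.02 the excess is 1 percentage point or less. This stands. It makes the finding conditional and keeps its size modest, but it does not supply a reason to assume the ICC is zero.

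A second reply is that the figures depend on the arm split. Blocks of 10 cannot hold an exact 2:1 ratio, and a larger treated arm shrinks the inflation. This also stands, and is why other splits are shown.

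A third is that about 3 groups cannot support a cluster model in an exploratory pilot of 40. That is a sound reason not to rely on an estimated random effect. It does not make the unadjusted error term right, and a fixed-ICC calculation avoids the difficulty.

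**Conclusion.** The point holds in conditional form. The plan delivers treatment in groups to one arm and analyses the women as independent. If the within-group correlation is positive, the planned tests reject more often than 5%. Under 13 v 27, normal data and ρ of 0.5 to 0.7, the interaction test runs at roughly 5.5–6% for ICC 0.02 and 8–10.5% for ICC 0.10. These are assumption-based figures, not documented ones. The matter limits how firmly the p-values can be read; it does not undermine the design.

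Three stronger readings are tempting and not supported:
- That the standard error is certainly too small and the 5% level certainly exceeded. The documents give no ICC, and at ICC 0 the test holds its level.
- That a reported confidence interval will be too narrow. Section 2.7 plans no confidence interval.
- That a later trial will inherit an understated error. No such trial is described.

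**What to change.** - Record each woman's CBT-I therapy group as a variable in the dataset.
- In section 2.7, add a sensitivity analysis of the between-arm difference in MARS-5 change from baseline, at post-intervention and at 12 weeks. Multiply the variance of the intervention-arm mean by 1 + (m − 1) × ICC, where m is the size-weighted mean of the actual group sizes and the ICC is on the change score. Use assumed values 0.02, 0.05 and 0.10, and report the results beside the unadjusted one. No pass-or-fail rule should hang on any one assumed value. Tying the multiplier to this two-arm contrast is necessary because it has no direct meaning for a 2x3 interaction F test.
- In section 3.1, state as a limitation that the ANOVA p-values ignore group delivery.
- A random effect for therapy group in the treated arm only, with small-sample degrees of freedom, may be added as optional and secondary.

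The cost is one variable, a short addition to 2.7 and one sentence in 3.1. The downside is a somewhat larger standard error (about 2%, 6% and 11% at the three ICC values with 13 v 27) and reliance on an ICC that has to be assumed.
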